a Participants who prematurely discontinue the study intervention (prior to completing the 24-week treatment period) should attend an Early Treatment Discontinuation (ETD) visit at earliest convenience with all the assessments planned for the End of Treatment visit (V5), except HRCT scans and IMP. In particular cases when the ETD visit is closed to a regular study visit, ETD could be merged and will replace the regular visit. In addition, the participants will be asked and encouraged to complete all the remaining study visits according to the visit schedule until and including the EOT visit (V5). Under exceptional circumstances when a participant cannot come to the site for the scheduled visit, a phone contact can be made after sponsor approval is given. During the phone contact, at least information about AEs and concomitant medication should be collected.

b Participants who prematurely discontinue the study should attend an Early Study Discontinuation (ESD) visit at earliest convenience with all the procedures planned for the End of Treatment Visit (Visit 5) except IMP. If the investigator considers that the time from the last HRCT scan exposure is not acceptable, the investigation will not be done.

c Post-treatment Follow-up: up to 12 Weeks or until the participants switch to commercialized dupilumab (or other biologic products), the call visit should be done first.

d Visit 6 will be a telephone visit. For the participants who switch to commercialized dupilumab (or other biologic products), the call visit should be done prior to the first injection with commercialized dupilumab (or other biologic products).

e Vital signs, including blood pressure (mmHg), heart rate (beats per minute), respiratory rate (breaths per minute), body temperature (degrees Celsius).

f A complete physical examination will include, at a minimum, assessments of the cardiovascular, respiratory, gastrointestinal and neurological systems and will be performed at V1, V2 and V5. Body weight (kg) will be measured at V1, V2 and V5. Height (cm) will be measured only at V1.

g Reversibility test: Three attempts may be performed during the screening period to meet the qualifying criteria for reversibility before randomization. This is only required if a reversibility test meeting eligibility criterion was not performed within 6 months prior to Visit 1.

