4 STUDY DESIGN

4.1 OVERALL DESIGN

This is a Phase 4 randomized, multinational study with a 24-week double-blind placebo-controlled period to explore the effect of dupilumab on airway inflammation through assessments of biomarkers, mucus plugging, and other lung imaging parameters in participants with asthma.

Study participation for each participant will be a total of minimum 29 weeks and up to 41 weeks.

The study includes 3 study periods:

- Screening period: 4 weeks (± 1 week), from signed informed consent to randomization.
- Randomized, placebo-controlled treatment period: 24 weeks from baseline (Day 1).
- Post treatment follow-up period: up to 12 weeks or until the participants switch to commercialized dupilumab (or other biologic products), whatever comes first.

Participants who fulfill the inclusion criteria and do not meet any of the exclusion criteria will be randomized (2:1) to one of the following investigational medicinal products (IMP).

- Dupilumab: participants will receive a loading dose of 600 mg of dupilumab (2 x 300 mg dupilumab SC on Day 1, followed by 300 mg every 2 weeks (Q2W) for 24 weeks.
- Placebo: participants will receive 2 x 2 mL placebo injections SC on Day 1, then 1 placebo injection Q2W for 24 weeks.

Randomization will be stratified by ICS dose level (medium/high- no less than 40% in 'high ICS' stratum) and region (Eastern Europe/ROW). In total, no more than 40% participants should be in "Eastern Europe" strata.

Study intervention discontinuation follow-up

Participants who prematurely discontinue the study intervention (prior to completing the 24-week treatment period) should attend an Early Treatment Discontinuation (ETD) visit at the earliest convenience with all the assessments planned for the End of Treatment (EOT) visit (V5), except HRCT and IMP. In particular cases when the ETD visit is close to a regular study visit, ETD could be merged and will replace the regular visit (See [Section 7.1.1](#)).

In addition, the participants will be asked and encouraged to complete all the remaining study visits according to the visit schedule until and including the EOT visit (V5).

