Any abnormal laboratory value will be immediately rechecked for confirmation before making a decision of definitive discontinuation of the IMP for the concerned participant.

Handling of participants after permanent study intervention discontinuation:

Participants who prematurely discontinue the study intervention (prior to completing the 24-weeks treatment period) should attend an ETD visit at earliest convenience with all procedures required at the EOT visit, except HRCT and IMP. In particular cases when the ETD visit is closed to a regular study visit, ETD could be merged and will replace the regular visit. In addition, the participants will be asked and encouraged to complete all the remaining study visits according to the visit schedule until and including the EOT visit (V5). Participants will be followed-up according to the study procedures specified in this protocol in SoA ([Section 1.3](#)). Under exceptional circumstances when a participant cannot come to the site for the scheduled visit, a phone contact can be made after sponsor approval is given. During the phone contact, at least information about AEs and concomitant medication should be collected.

All cases of permanent discontinuation of study intervention should be recorded by the Investigator in the appropriate pages of the e-CRF when considered as confirmed.

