8.1.1. Primary analysis

Proportion of participants achieving FeNO <25 ppb at week 24 will be analyzed with a Cochran-Mantel-Haenszel (CMH) test adjusted by stratification factors (ICS dose level at baseline and region). Comparison of the proportions of responders between dupilumab and placebo will be derived, and corresponding odds ratios and 95% CI along with the p-value will be reported.

For participants who discontinued the study treatment not due to COVID-19 pandemic, off-treatment data will be used to determine the responder/non-responder status. For any participants who discontinued the study treatment due to COVID-19 pandemic, off-treatment data will be set to missing. Missing data at week 24 will be considered as non-responders.

Percent change from baseline in untrimmed distal [s]iVaw at TLC will be analyzed with a MMRM model under the MAR framework. The MMRM model will use percent change from baseline in untrimmed distal [s]iVaw up to week 24 as response variable and include study intervention (dupilumab, placebo), baseline value of untrimmed distal [s]iVaw at TLC, region (EE/ROW), ICS dose level (medium/high), visits (up to week 24), study intervention by visit interaction, and baseline untrimmed distal [s]iVaw at TLC by visit interaction terms all as fixed effects. An unstructured correlation matrix will be used to model the within-participant errors.

The Kenward-Roger approximation (ddfm=kr) will be used to estimate the denominator of degrees of freedom. Parameters will be estimated using restricted maximum likelihood method with the Newton-Raphson algorithm. The adjusted LS mean in percent change from baseline of each study intervention group, the LS mean difference between the dupilumab and placebo groups, and the corresponding SEs and 95% CIs will be provided at all scheduled visits. The p-value corresponding to the LS mean difference will be provided at Week 24 only.

For participants who discontinued the study intervention before Week 24 not due to the COVID-19 pandemic, off-study intervention imaging data measured up to Week 24 will be included in the analysis. In contrast, for any participants discontinuing the study intervention due to the COVID-19 pandemic, off-study intervention data will not be included (ie, set to missing) but will be assumed missing at random.

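### A treatment-discontinuation visit that excludes HRCT may replace Visit 5, so a participant who stops dosing just before Week 24 can miss the scan for the second primary endpoint while in clinic

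*Protocol*

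**What the plan says.** Protocol 1.3, footnote a, defines the ETD visit as one "with all the assessments planned for the End of Treatment visit (V5), except HRCT scans and IMP". Protocol 4.1 ("with all the assessments planned for the End of Treatment (EOT) visit (V5), except HRCT and IMP") and 7.1.1 ("with all procedures required at the EOT visit, except HRCT and IMP") say the same, and SAP 15.2, footnote a, repeats it.

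All four places then give the merging rule. Footnote a reads: "In particular cases when the ETD visit is closed to a regular study visit, ETD could be merged and will replace the regular visit". Protocol 4.1 has it as: "In particular cases when the ETD visit is close to a regular study visit, ETD could be merged and will replace the regular visit". No number of days defines how near the visits must be, and nothing says what happens to a scan due at the replaced visit. The next sentence encourages participants to "complete all the remaining study visits according to the visit schedule until and including the EOT visit (V5").

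Protocol 2.3 schedules three HRCT scans per participant, at Day 1, Week 4 (V3) and Week 24 (V5). Visit 6 is a telephone visit.

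On the analysis side, SAP Table 2-2 applies a treatment-policy strategy to discontinuation not caused by COVID-19. For [s]iVaw at TLC, SAP 8.1.1 states that "off-study intervention imaging data measured up to Week 24 will be included in the analysis".

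The early study discontinuation (ESD) visit in Protocol 7.2 excludes only study drug. HRCT is kept there unless the investigator finds the time since the last scan unacceptable.

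**The concern.** The visit rule and the estimand pull in different directions. Treatment policy needs a Week 24 scan from people who have stopped dosing. The merging rule can remove that scan when the person is in the clinic at about the right time and every other V5 assessment is being done.

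Three analyses depend on the Week 24 scan: the second primary endpoint (percent change in untrimmed distal [s]iVaw at TLC) and the two secondary endpoints in the SAP 8.2.5 hierarchy (UCSF mucus score and trimmed distal [s]iRaw at TLC). FeNO, the first primary endpoint, is measured at the ETD visit and is unaffected.

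A scan lost this way is missing because treatment was stopped. The MMRM handles it as missing at random, and the multiple-imputation sensitivity analysis in SAP 8.1.5 makes the same assumption. Collecting the value is better than relying on that assumption, particularly for an endpoint planned with only about 64% power.

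**Working it through.** **Step 1. Follow the text for each merge.**

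| Case | HRCT due at the replaced visit | Later on-site visit with HRCT | What is lost on a literal reading |
|---|---|---|---|
| ETD replaces V3 (Week 4) | Yes | V5 | Week 4 value only |
| ETD replaces V4 (Week 12) | No | V5 | Nothing |
| ETD replaces V5 (Week 24) | Yes | None (V6 is by telephone) | Week 24 value |
| ETD not merged | Not applicable | V5, if attended | Nothing |

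Only the V5 merge removes the endpoint scan. In the V3 case the participant still has V5 ahead. SAP 8 admits to the model anyone with a baseline and at least one post-baseline value, so that participant drops out only if Week 24 is also missing.

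**Step 2. Check the analysis windows.** SAP 15.5 allocates FRI data from Day 2 to Day 98 to Week 4, and from Day 99 onward to Week 24. A scan at a merged late visit, or at a separate V5, would therefore count as Week 24. The windows cannot help if no scan is taken.

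**Step 3. Reproduce the plan's figures.** Evaluable participants: 87, at 10% dropout. Number to randomise: 87 / (1 − 0.10) = 96.7, rounded up to 97, which matches. A 2:1 split of 87 gives 58 and 29, which also matches. The 64% power in Protocol 9.2 cannot be checked, because the assumed difference and SD are redacted.

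**Step 4. Size per lost scan (illustration).** Solve the two-sample t-test (58 vs 29, two-sided 0.05) for the standardised effect d that gives 64% power. The noncentrality is d / √(1/n₁ + 1/n₂) on n₁ + n₂ − 2 degrees of freedom. The solution is d = 0.533, with noncentrality 0.533 / √(1/58 + 1/29) ≈ 2.34 on 85 df. Hold d fixed and count each lost scan as a full loss:

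| Week 24 scans lost (dupilumab + placebo) | n per arm | Power |
|---|---|---|
| 0 + 0 | 58 / 29 | 64.0% |
| 1 + 0 | 57 / 29 | 63.7% |
| 0 + 1 | 58 / 28 | 63.0% |
| 3 + 0 | 55 / 29 | 63.2% |
| 2 + 1 | 56 / 28 | 62.4% |
| 0 + 3 | 58 / 26 | 60.8% |

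One lost scan costs about 0.3 points on dupilumab (64.0 − 63.7) and about 1 point on placebo (64.0 − 63.0). Three lost scans, an assumed count, leave 60.8% to 63.2% depending on arm.

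**The case against.** The strongest reply is that no passage tells a site to skip the V5 scan. Merging is optional and reserved for particular cases. Merging could also mean doing both visits' procedures. Participants are still encouraged to attend up to and including V5, and Protocol 7.1.1 keeps them in the study for efficacy evaluation. It also calls permanent discontinuation rare. This stands against any claim that the scan is certain to be lost. It does not remove the gap: once visits are merged, the text says the ETD visit *will* replace the regular one, the ETD visit is defined without HRCT, and a replaced V5 is no longer a remaining visit. Two sites could read this differently for a primary-endpoint measurement.

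It may also be said that the contrast with the ESD visit is weak, since that visit is the last chance to scan and an ETD visit usually is not. That is fair for a stand-alone ETD visit, where excluding HRCT avoids an extra scan. It is not an answer when ETD replaces V5, because then this too is the last on-site visit.

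The protocol's analysis text includes off-treatment imaging only as available. That tolerates missing scans but is no reason to create them.

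A reader might infer more than the documents support:
- **That a Week 4 merge loses the endpoint.** It does not, because V5 is still due.
- **That late stoppers differ most from completers, so the bias is large.** The documents give no evidence for this. Someone who stops near Week 24 has had almost all planned dosing and might differ little.
- **That the power figures are a forecast.** The count is assumed, and some of these participants may already be among the 10 (97 − 87) allowed for dropout.

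**Conclusion.** The point holds as a gap in a stated rule with an avoidable cost, not as a certain loss of data. When an ETD visit replaces V5, a literal reading omits the Week 24 HRCT and leaves no on-site visit to recover it. That works against the treatment-policy handling of the second primary endpoint and also affects both gated secondary endpoints.

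The numerical effect is probably small. The documents do not say how many visits would be merged. The cost of about 0.3 to 1 power point per scan rests on two assumptions: d of about 0.53, back-solved from a power figure whose inputs are redacted, and full loss of each affected participant. The MMRM would recover part of it from a Week 4 scan. Any bias is unquantified, and its direction cannot be inferred from the documents. The case for acting is that the missingness is linked to discontinuation, is easily prevented, and falls on an endpoint with little power to spare.

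**What to change.** Reconcile Protocol 1.3 footnote a, 4.1 and 7.1.1, and SAP 15.2 footnote a:
- Limit the HRCT exclusion to stand-alone ETD visits.
- State that when the ETD visit is merged with V3 or V5, the HRCT scheduled at that visit is still performed.
- Extend to merged visits the investigator opt-out on time since the last scan that the ESD visit already has.

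Stating how near the visits must be for merging would also help sites apply the rule uniformly.

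The cost is a short amendment and a site memo. No participant receives a scan beyond the three already planned, and the statistical model and analysis windows need no change.

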h Asthma Control Questionnaire-7 (ACQ-7): items 1 to 6 should be completed by the participant, independently from their physician, the study nurse or any other medical personnel and without any help from friends or relatives. The questionnaire should be completed by the participants before the consultation and/or clinical tests, in a quiet place. ACQ-5 scores (mean of the responses to the first 5 questions) and ACQ-6 (mean of the responses to the first 6 questions) will be derived from ACQ-7. The local values of FEV1 will be considered for the ACQ-7 scores. For the statistical analysis we will use centrally read values.

i Asthma Quality of Life Questionnaire with Standardized Activities [AQL Q(S)] should be completed by the participant, independently from their physician, the study nurse or any other medical personnel and without any help from friends or relatives. The questionnaire should be completed by the participants before the consultation and/or clinical tests, in a quiet place.

j FeNO should be conducted prior to spirometry and the participant should refrain from eating and drinking for ≥ 1 hour before the procedure. The test will be performed after a wash out period of bronchodilators according to their action duration as detailed in [Table 4 \(Section 8.1\)](#). Retesting of FeNO can be done one additional time during screening if the eligibility criterion for FeNO was not met at V1. FeNO will be rechecked at randomization visit (V2) for eligibility. Further details on the procedure for measuring FeNO will be provided in a separate instruction manual.

k Centrally read. Scans are respiratory gated to avoid variations in lung and airway volume, as per scans protocol. Further details on the HRCT scan will be provided in a separate instruction manual. The wash out time of the asthma controllers and rescue medication before HRCT and lung function assessments is detailed in [Table 4 \(Section 8.1\)](#). If HRCT scan cannot be performed at D1 due to logistic reasons, it can be scheduled the next day. In this particular situation the investigator should ensure that the IMP loading dose is administered after the HRCT scan, at D1+1 day. At visits, the HRCT scan can be done before spirometry or before post-BD FEV1 or after (in the latter case the wash-out period of SABA should be ensured), as per investigator's decision.

l FOT should be conducted prior to spirometry. Further details on FOT will be provided in a separate instruction manual.

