m Centrally read. Spirometry test should be performed before IMP administration, in the morning if possible, but if testing can only be done at another time during the day, then the testing should be done at approximately the same time of day at each visit throughout the study. Spirometry will be performed after a wash out period of bronchodilators according to their action duration as detailed in [Table 4 \(Section 8.1\)](#). This will be verified before performing the measurements. A participant who is unable to complete a successful spirometry effort as defined by ATS criteria or evaluated by the investigator or did not meet the eligibility criterion for pre-BD FEV1 at V1 can be retested one additional time during the screening period. For spirometry the investigator will assess the eligibility based on the FEV1 local values from V1 and V2 before randomization (the results from central reading will not be available on the same day). The recommendation is to perform the FeNO and FOT before spirometry

n Serum pregnancy test at screening visit (Visit 1) and urine pregnancy tests at the other visits using dipstick. A negative result must be obtained at Visits 1 and 2 for eligibility. In case of positive urinary test during the study, a serum pregnancy test should be performed as soon as possible to confirm the pregnancy. A urine pregnancy test will be performed at home at the end of follow-up visit.

o Retesting of eosinophil count is allowed up to three times during the screening period to meet inclusion criteria for showing eosinophil count ≥ 300 cells/microliter (cells/mL) (1.06) before randomization. This is only required if the participant does not have the blood eosinophil count measured within 6 months prior to V1 in the absence of OCS treatment.

p Hepatitis screening covering hepatitis B surface antigen (HBs Ag), total hepatitis B core antibody (total HBcAb) including IgM HBcAb; hepatitis C virus antibodies (HCvAb). In case of results showing HBsAg (negative) and HBcAb (positive), HBV DNA testing will be performed to rule out a false positivity or to clarify the serological status if the investigator finds it unclear to interpret in absence of known HBV infection. In case of results showing HCvAb (positive), HCV RNA testing may be performed to rule out a false positivity. Human immunodeficiency Virus (HIV) screening (Anti-HIV-1 and HIV-2 antibodies).

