This study in patients with asthma aims to gain insight into the effect of dupilumab on airway changes and on lung function improvement. The combination of clinical outcomes (FEV₁), Asthma Control Questionnaire (ACQ), forced oscillometry (FOT), biomarkers (FeNO) and functional imaging will provide further characterization of dupilumab's unique mechanism of action (MoA). The study is medically and scientifically justified. The imaging study is designed to fulfill an unmet need by providing further insights into how dupilumab may improve lung function and reduce airway inflammation, and if the aims are achieved, it will help HCPs understanding dupilumab's MoA, therefore supporting optimal therapeutic management.

The functional imaging will be performed using HRCTs which will provide scientifically useful information on bronchodynamics and hyperinflation, airway resistance, airway wall thickness, ventilation defects, mucus plugging that cannot be obtained with another method.

The protocol entails that each participant will receive 3 HRCT scans (at D1, W4 and W24), each comprised by 2 acquisitions, respectively on full inspiration (total lung capacity) and end expiration (functional residual capacity) utilizing respiratory gating. Therefore, each participant will be exposed to a total of 6 HRCT acquisitions.

The effective radiation dose estimated from each research HRCT, assuming an average acquisition protocol in a modern CT scanner (at least 64 slices with radiation reduction options) is approximately 1.8 mSv. Assuming 6 HRCT acquisitions per participant, the average cumulative dose per participant will be approximately 10.8 mSv (30, 31, 32, 33).

The natural background radiation exposure from natural sources is approximately 3.0 mSv. Hence, total radiation from the CT scans in this study is approximately equal to less than 3.5 years of exposure to natural background radiation.

The Health Physics Society recommends against quantitative estimation of health risks below an individual dose 50 mSv in one year, given that the risks of health effects are either too small to be observed or are nonexistent.

Radiation-related risks due to HRCT are exclusively stochastic effects, primarily cancer induction, given that current diagnostic doses of less than 10 mSv are well below the threshold for deterministic effects, which generally start at 2000 mSv (2 Gy) (2, 3).

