5.1 INCLUSION CRITERIA

Participants are eligible to be included in the study only if all of the following criteria apply:

Age

I 01. 18 to 70 years of age inclusive with the diagnosis of asthma based on Global Strategy for Asthma Management and Prevention (GINA) 2019 ([1](#)) at the time of signing the informed consent.

Type of participant and disease characteristics

I 02. History of ≥ 1 exacerbation(s) in the previous year before V1.

Exacerbation is defined as deterioration of asthma that results in emergency treatment, hospitalization due to asthma, or treatment with systemic steroids.

I 03. Uncontrolled moderate-to-severe asthma (ACQ-5 ≥ 1.5) at V1 and V2, prior to randomization.

I 04. Pre-bronchodilator FEV₁ $\leq 80\%$ of predicted normal at V1 and V2, prior to randomization.

I 05. Exhibit bronchodilator reversibility ($\geq 12\%$ and 200 mL improvement in FEV₁ post SABA administration) during screening, prior to randomization.

I 06. Blood eosinophil ≥ 300 cells / μ L and FeNO ≥ 25 ppb during screening and prior to randomization.

NOTES:

- Historical values of blood eosinophil count meeting the eligibility criterion measured within 6 months prior to SV1 in the absence of OCS treatment are allowed.
- FeNO value to be checked for eligibility at V2 as well.

I 07. Existing treatment with medium to high dose ICS in combination with a second controller (eg, LABA, LTRA) \pm a third controller. The dose regimen should be stable ≥ 1 month prior V1 and during screening.

I 08. Willing and able to comply with all clinic visits and study related procedures.

Weight

Not applicable.

Sex

I 09. Male and Female

Contraceptive used by men or women should be consistent with local regulations regarding the methods of contraception for those participating in clinical studies.

Female participants of childbearing potential are eligible to participate if they agree to use a highly effective method of contraception consistently and correctly during the intervention period and up to 12 weeks after last dose of study intervention or until the participants switch to commercialized dupilumab (or other biologic products), whatever comes first, as described in [Section 10.4](#) (Appendix 4).

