5.4 SCREEN FAILURES

Screen failures are defined as participants who consent to participate in the clinical study but are not subsequently eligible to be randomized. A minimal set of screen failure information is required to ensure transparent reporting of screen failure participants to meet the Consolidated Standards of Reporting Trials (CONSORT) publishing requirements and to respond to queries from regulatory authorities. Minimal information includes demography, screen failure details, eligibility criteria, and any SAE.

Reasons for screen failure may be unfulfilled eligibility criteria and withdrawal of consent during screening period, between screening and randomization.

Participants who do not meet the eligibility criteria for participation in this study and for whom resolution of the screen failure reason may not be expected within a reasonable time frame, will be deemed as screen failure.

Rescreening: The participants may be rescreened once during the open screening period and all the screening procedures will be repeated; a different participant identification number will be issued.

There is no requirement for a waiting period between the screen failure date and the rescreening date. The Interactive voice recognition system (IVRS)/ Interactive web response system (IWRs) report will flag rescreened participants. Participants that are rescreened must sign a new consent form and all Visit 1 procedures must be repeated.

Retesting: If certain dynamic laboratory tests do not meet the eligibility criteria, these laboratory assessments may be repeated, at the discretion of the Investigator, if it is judged that they are likely to return to acceptable range for study inclusion within the screening visit window (21 to 35 days) prior to Day 1. These participants do not need to sign a new ICF and a new participant number will not be allocated.

Retesting of eosinophil values is allowed up to 3 times during the screening period to meet inclusion criteria for showing eosinophil count ≥ 300 cells/ μ L ([I 06](#)) before randomization. This is only required if the participant does not have the blood eosinophils measured within 6 months prior to V1 in the absence of OCS treatment.

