A high mucus score (plugs in ≥ 4 segments) occurred in 67% of subjects with asthma with FEV₁ of less than 60% of predicted volume, 19% with FEV₁ of 60% to 80%, and 6% with FEV₁ greater than 80% ($P < 0.001$). N=146, among those 96 were severe asthma participants (65%) (39).

Functional Respiratory Imaging can accurately assess the regional airway closures induced by mucus plugs and the re-opening of airways due to intrapulmonary percussive ventilation in COPD participants (40).

Airway wall thickness

Asthmatics have increased airway wall volumes due to inflammation compared to healthy individuals.

The airway wall volume/airway lumen ratio parameter can be derived from the FRI parameters airway wall volume and airway volume. Airway wall thickness can be derived from this as well (and can be shown in discreet locations).

After a treatment with ICS in asthma an increase in airway lumen volume (iVaw) and a reduction in airway wall volume (iVaww) can be observed. The effect size of iVaw is larger than effect size iVaww due to the better resolution of iVaw in HRCT. Similar findings were observed by Haldar et al when studying Mepolizumab (41).

Lobar volumes

By identifying and grouping the voxels that represent the air in the lungs, the lung volume (L) can be determined from the scans at both FRC and TLC. During segmentation, identifying the fissure planes on the CT images and using these surfaces as cutting objects can separate lung lobes. Therefore, not only the total lung volume is determined, but also the volume of each lobe individually, which allows to pick up substantial regional physiological changes of the airways and the lobe volumes.

The HRCT scans assessment will be performed by central reading. Further details on the procedure will be provided in a separate instructions manual. The wash out period of asthma controllers and rescue medication before HRCT scan is detailed in the [Table 4 \(Section 8.1\)](#).

If HRCT scan cannot be performed at D1 due to logistic reasons, it can be scheduled the next day. In this particular situation the investigator should ensure that the IMP loading dose is administered after the HRCT scan, at D1+1 day.

At visits, the HRCT scan can be done before spirometry or before post-BD FEV1 or after spirometry (in the latter case the wash-out period of SABA should be ensured), as per Investigator's decision.

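### The Day 1 HRCT may be done before the V2 FEV1 and pregnancy-test results that decide eligibility, so a screen failure can be scanned for no analysed data

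*Protocol*

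**What the plan says.** **Scan order.** Footnote k of the Schedule of Activities (Protocol 1.3) says: "At visits, the HRCT scan can be done before spirometry or before post-BD FEV1 or after", at the investigator's discretion. Protocol 8.1 says the same: "At visits, the HRCT scan can be done before spirometry or before post-BD FEV1 or after spirometry". SAP 15.2 reproduces the footnote. None of the three treats Day 1 differently from Weeks 4 and 24.

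**Eligibility at V2.** Criterion I 04 requires pre-bronchodilator FEV1 at or below 80% "of predicted normal at V1 and V2, prior to randomization". Footnote m makes the local reading decisive: "For spirometry the investigator will assess the eligibility based on the FEV1 local values from V1 and V2 before randomization". Footnote n requires a negative pregnancy test at both V1 and V2; the V2 test is a urine dipstick. Criterion I 03 sets an ACQ-5 threshold at both visits. The note to I 06 adds FeNO: "FeNO value to be checked for eligibility at V2 as well".

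**Exposure.** Protocol 2.3 states that "each participant will receive 3 HRCT scans (at D1, W4 and W24), each comprised by 2 acquisitions", and concludes: "Therefore, each participant will be exposed to a total of 6 HRCT acquisitions". It puts each acquisition at about 1.8 mSv and the average cumulative dose at about 10.8 mSv. The expert review in Appendix 10 considers up to 6 acquisitions per patient.

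**Rescreening.** Protocol 5.4: "The participants may be rescreened once during the open screening period and all the screening procedures will be repeated". A new participant number is issued.

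**The concern.** The first HRCT falls on the day when eligibility is finally settled. If the scan comes first, a research exposure is given before it is known whether the person can be randomised. Someone who then fails is a screen failure. Protocol 9.3 limits the efficacy population to randomised participants, and the minimum screen-failure data in Protocol 5.4 include no imaging, so the scan serves no planned analysis.

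The procedures also do not guarantee the exposure ceiling that the risk section and the expert reviewed, because nothing says whether a Day 1 scan already taken is reused, repeated or counted when the person is rescreened.

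Elsewhere the protocol does limit avoidable scans. The early treatment discontinuation visit omits HRCT, and at the early study discontinuation visit the investigator may omit it if the last exposure was too recent. V2 has no comparable safeguard. What is at stake is avoidable exposure and the accuracy of the stated total, not bias in the treatment comparison.

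**Working it through.** **1. Which V2 results can come after the scan?**

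| V2 eligibility item | Order relative to HRCT |
|---|---|
| ACQ-5 (I 03) | Questionnaire completed before clinical tests (footnote h; Protocol 8.1) |
| FeNO (I 06) | Before HRCT in SAP 15.12; the protocol places it only before spirometry (footnote j; 8.1) |
| Local pre-bronchodilator FEV1 (I 04, footnote m) | May follow HRCT (footnote k; 8.1) |
| Urine pregnancy test (footnote n) | No order stated |

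The open items are FEV1, where the later order is expressly allowed, and the pregnancy test, where no order is given. For FeNO the two documents differ.

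**2. Does another rule close the gap?** Protocol section 8 requires screening evaluations to be completed and reviewed against the eligibility criteria. It does not time that review relative to the HRCT.

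**3. The plan's own figure.** Inputs from Protocol 2.3: 3 scans, 2 acquisitions per scan, 1.8 mSv per acquisition.

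- Acquisitions: 3 × 2 = 6.
- Dose: 6 × 1.8 = 10.8 mSv. Both stated figures are reproduced.

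**4. The paths that the text leaves open.** The last column uses the unrounded dose from the Appendix 10 inputs, 135 mGy·cm × 0.014 = 1.89 mSv per acquisition.

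| Path | Acquisitions | At 1.8 mSv | At 1.89 mSv |
|---|---|---|---|
| Scanned first, fails V2 | 2 | 3.6 mSv | 3.8 mSv |
| Scanned first and fails V2, on both screenings | 4 | 7.2 mSv | 7.6 mSv |
| As planned | 6 | 10.8 mSv | 11.3 mSv |
| Scanned first, fails V2, rescreened, baseline scan repeated, randomised, all scans done | 2 + 6 = 8 | 14.4 mSv | 15.1 mSv |

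The last path exceeds the stated total by (14.4 − 10.8) / 10.8 = 33%. I do not scale the expert's lifetime risk estimate to 8 acquisitions, because Appendix 10 says that risk is not linear in total dose.

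**5. How many people?** The number scanned for no data is (people reaching V2) × (share scanned before eligibility is settled) × (share of those who then fail). The documents give none of the three. If every site does spirometry and the pregnancy test first, the number is zero.

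**6. If the Day 1 scan follows the V2 results.** A person who fails V2 has 0 acquisitions at that visit, and a rescreened person who completes the trial has 6.

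**The case against.** - **The order is optional.** A site that does spirometry first never meets the problem. This stands, and it is why no count can be given. It does not remove the permission.
- **FeNO and ACQ-5 are already handled.** Largely true. A reader might infer that every V2 criterion can be assessed after the scan. The documents do not support that: the questionnaire precedes clinical tests, and SAP 15.12 puts FeNO before the HRCT. What remains for FeNO is that the protocol, which sites follow, does not carry the SAP's order.
- **A repeat baseline scan is not stated.** Protocol 5.4 repeats the screening and Visit 1 procedures, and the HRCT is not a Visit 1 procedure. A second Day 1 scan follows from the schedule and from the absence of any reuse rule. A reader might infer that every rescreened person exceeds 6 acquisitions; that happens only if each step of the path above occurs.
- **The dose figure is an average.** Protocol 2.3 calls 10.8 mSv an approximate average and also relies on a 50 mSv per year threshold, which 14.4 mSv does not approach. So it would be wrong to infer that the benefit/risk conclusion is overturned. The narrower point stands: 8 acquisitions were not assessed.
- **Fixing the Day 1 order could create a mismatch.** If baseline is scanned after forced spirometry and follow-up before it, the percent change in [s]iVaw might be affected. This is fair, but the present free order already allows it, and using one order per participant deals with it.
- **The HRCT instruction manual may set the order.** It was not available for this review. Even if it does, the protocol's express permission would need to be brought into line.

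**Conclusion.** The concern holds in a limited form. The protocol expressly allows the Day 1 HRCT before the V2 FEV1 result, and sets no order between the scan and the V2 pregnancy test. A person scanned first who then fails receives about 3.6 mSv with no planned use of the images. In the conditional rescreening path the total is 8 acquisitions, about 14.4 mSv, against the 6 and about 10.8 mSv that were assessed.

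These sizes rest on the protocol's 1.8 mSv per acquisition. The 8-acquisition case also rests on the baseline scan being repeated at rescreening, which the documents imply but do not state. A reader might want a V2 failure rate or a number of people exposed. Neither can be derived, because the documents give no failure rate and no share of sites that scan first, so none should be quoted.

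The change should be made, because it is cheap and prevents avoidable exposure. It does not affect the validity of the efficacy comparison.

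**What to change.** 1. In footnote k of Protocol 1.3, in Protocol 8.1 and in SAP 15.2, state that on Day 1 the HRCT is done only once the V2 ACQ-5, FeNO, local pre-bronchodilator FEV1 and urine pregnancy test results are available and meet the criteria. The slot before post-bronchodilator FEV1, or the existing next-day option, can be used. The requirement that the scan precede the loading dose is unchanged.
2. Keep the same order of scan and spirometry at Weeks 4 and 24 where feasible, so that baseline and follow-up scans are comparable.
3. Carry the FeNO-before-HRCT order of SAP 15.12 into the protocol.
4. In Protocol 5.4, state whether an earlier Day 1 scan is reused or repeated at rescreening and how it counts toward the 6 acquisitions. Reconcile this with Protocol 2.3 and Appendix 10.

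Cost: a few sentences, with no new visit or test and no change in sample size. Sites lose some freedom in booking the scanner on Day 1. The next-day option is now worded for logistic reasons, and it means that the Table 4 washout conditions must also be met on that day.
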